9.1. Safety endpoints: serious adverse events and suspected unexpected serious adverse reactions

The safety endpoints of this study are:

- Hospital admissions for any reason involves staying at a hospital for at least one night or more for medical reasons. It includes admissions to hospital wards and overnight stays in emergency departments.
- Intensive Care Unit admission for any reason involves staying at ICU for at least one night.
- Death for any reason while the participant is being followed during the clinical trial.

Based on previous experience and randomized controlled trials in adult and elderly individuals, the risks of BCG vaccination are considered low. The expected local reaction after successful vaccination with BCG

Vaccine "AJ Vaccines" is injection site swelling followed by a local lesion that can form an ulcer after 2-4 weeks and heal after a few months, leaving a small flat scar. Redness and tenderness may occur at the injection site. Regional swelling of the lymph node <1 cm may also occur. Not common ($\geq 1/1,000$ to $< 1/100$) and rare ($\geq 1/10,000$ to $1/1,000$) adverse reactions: blood and lymphatic system - regional swelling of lymph nodes > 1 cm; nervous system disorders – headache; bones, joints, muscles and connective tissue – osteitis; infections and parasitic diseases - suppurative lymphadenitis, osteomyelitis, BCGitis; abscess at the injection site. We will specifically enquire about adverse events at the biweekly interviews and in the end questionnaire. It is common and not treatment-demanding that, following BCG vaccination, redness, swelling and ulceration of the skin where the vaccine is given will occur. There may be swollen lymph nodes in the area some weeks after the vaccine is given, and in the longer term, a small ~5 mm diameter scar will appear where the vaccine was given. For the descriptive analysis of adverse events, we used counts (percentage) for categorical variables and mean (standard deviation) or median (interquartile range) for continuous variables. For the comparison of adverse events between the two groups studied proportions will be compared using the chi-square test (χ^2 test (categorical variable) or Student's t-test or Mann-Whitney test (quantitative variable) according to the distribution of variables. Statistical significance was set at the 5% level (two-tailed tests) and 95% confidence intervals (95%CI) for the estimates.

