- The injection needle is held almost parallel to the skin surface and inserted slowly with the oblique edge pointing upwards, approx. 2 mm down into the upper skin layer.
- The needle should be visible through the epidermis at insertion.
- Vaccination should be performed slowly.
- The appearance of a pale bladder is evidence of proper injection technique.
- The injection site should be uncovered to promote healing.
- The administration of the saline solution will follow the exact same procedure.

Follow-up

Follow-up will last for 6 months (182 days). Every second week, participants will be contacted over telephone and interviewed for symptoms and absenteeism from work. By the end of follow-up, participants will be invited for another POC test for COVID-19 serology.

Figure 2 - Flowchart

In case of not answering the telephone call and questionnaire for ≥ 18 days, information on the participant will be retrieved from hospital registries for absenteeism and hospital admission registries, ICU admission and outcomes. An explicit permission for this procedure will be requested from the participant during informed consent procedures at enrolment.

Participant timeline

	Staff member	Enrolment	Follow-up	End of Follow-up
--	--------------	-----------	-----------	------------------

		(W1)	(W2 to W25)	(W26)
Consent form	Research assistant	x		
Inclusion/exclusion criteria form	Research assistant	x		
POC test for COVID antibodies	Study nurse	x		
Randomization	Study nurse	x		
Administration of intervention	Study nurse	x		
Baseline questionnaire	Research assistant	x		
Follow-up Interview	Research assistant		x	
End questionnaire	Research assistant			x

Data management

The researchers will archive the published articles and the final peer-reviewed manuscripts in an online repository before, if feasible, at the same time as, or after publication in open access mode. The researchers will also make their data available according to the Open Research Data Pilot (ORD pilot) of the Horizon 2020 program.

Study management, monitoring and quality control

The project will be led by an International Steering Committee (ISC) consisting of PIs in each of the five countries involved: [name], PI from Guinea-Bissau; [name] (international coordinator), PI from Denmark; [name], PI from Portugal; [name], PI from Cape Verde; and [name], PI from Mozambique.

Figure 3 - Organogram of management structures

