Spearheaded by the Dutch group, a platform is now being established for a meta-analysis to be done immediately (i.e. within one week) after the first trial yields a significant result. The meta-analysis will include all ongoing trials except for the one yielding the significant result. If the meta-analysis confirms the effect (i.e. statistically significant difference at a two-sided p-value < 0.05) the recommendation will be to offer BCG to HCW or to stop trials. If it is not confirmed, the recommendation will be to continue all trials. The result of the interim analysis will be made public to inform health authorities.

A Data Transfer Agreement has been established to allow anonymous sharing of our data to contribute to this meta-analysis.

Safety

Intervention consist of intradermal administration of a standard dose of BCG vaccine or placebo (saline). Based on previous experience and randomized controlled trials in adult and elderly individuals, the risks of BCG vaccination are considered low. It is common and not treatment-demanding that, following BCG vaccination, redness, swelling and ulceration of the skin where the vaccine is given will occur. There may be swollen lymph nodes in the area some weeks after the vaccine is given, and in the longer term, a small ~5 mm diameter scar will appear where the vaccine was given.

Severe but very rare side effects are injection site abscesses, BCG lymphadenitis (simple or suppurative, disseminated BCG disease, osteitis, osteomyelitis, anaphylaxis, formation of keloid/lupoid. They are so rare that it would be unlikely with cases in the present trial of 1050 participants, but we will specifically enquire about adverse events at the weekly interviews and in the end questionnaire. In the case of adverse events they will be reported to the vaccine producer and the patient will be receive treatment.

Temporary halt for reasons of subject safety: In accordance to section 10, subsection 4, of the Medical Research Involving Human Subjects Act (WMO), the sponsor will suspend the study if there is sufficient ground that continuation of the study will jeopardize subject health or safety.

The sponsor will notify the EC without undue delay of a temporary halt including the reason for such an action. The study will be suspended pending a further positive decision by the EC and the DKMA. The investigator will take care that all subjects are kept informed.

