Adverse events (AEs): defined as any undesirable experience occurring to a subject during the study, whether or not considered related to the investigational product, the placebo or the trial procedures, will be biweekly assessed during the mobile phone interviews. All adverse events will be reported to the relevant authorities according to existing national notification procedures.

Serious adverse events (SAEs) is any untoward medical occurrence or effect that results in death, is life threatening or requires hospitalization or prolongation of existing inpatients' hospitalization, results in persistent or significant disability or incapacity, is a congenital anomaly or birth defect or any other important medical event due to the intervention based upon appropriate judgement by the investigator. An elective hospital admission will not be considered as a serious adverse event.

Participants will be asked about the occurrence of SAE's biweekly in the questionnaire. In case of a SAE, dependent on the symptoms of the participant, he/she will be contacted by the investigator and if necessary, admitted to the hospital. The condition of the participant will be evaluated by the investigator, who can decide to un-blind if deemed necessary.

The investigator will notify sponsor and DSMB within 24 hours after first knowledge of any SAEs, in order for DSMB and sponsor to assess whether it is a suspected unexpected serious adverse reactions (SUSAR).

Unexpected adverse reactions are SUSARs if the event is serious, if there is a certain degree of probability that the event is a harmful and an undesirable reaction to the medicinal product under investigation, regardless of the administered dose and it is unexpected, that is to say, the nature and severity of the adverse reaction is not in agreement with the product information as recorded in the summary product characteristics.

The investigator and the sponsor will report to the EC and competent national authorities.

Beneficence

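### SAP 9.1 is headed SAEs and SUSARs, but its only endpoints are all-cause overnight admission, an ICU night and death; these do not match the protocol's SAE definition and are not split by relatedness

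*SAP*

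**What the plan says.** The SAP section is titled "9.1. Safety endpoints: serious adverse events and suspected unexpected serious adverse reactions". It then lists three endpoints as the safety endpoints of the study:

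- all-cause admission: "Hospital admissions for any reason involves staying at a hospital for at least one night or more for medical reasons"
- intensive care: "Intensive Care Unit admission for any reason involves staying at ICU for at least one night"
- mortality: death from any cause during the participant's follow-up

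The same section says that adverse events are asked about at the two-weekly calls and in the end questionnaire, and that they are compared between arms with a chi-square test (or a t or Mann-Whitney test for quantitative variables). It gives no split by seriousness or by relation to the vaccine.

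The protocol's Safety section defines an SAE by death, threat to life, hospitalisation or its prolongation, and lasting disability. It adds that an SAE also "is a congenital anomaly or birth defect or any other important medical event due to the intervention", on the investigator's judgement. It further states: "An elective hospital admission will not be considered as a serious adverse event". SAEs are asked about every two weeks. Each one goes to the sponsor and the DSMB within 24 hours, to be assessed as a possible SUSAR.

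Reducing admissions is a secondary objective of the SAP. Admission for illness is a secondary outcome, and all-cause ICU admission and all-cause death are among its other outcomes. All three event types have rows in SAP Table 5.

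**The concern.** The heading promises an analysis of SAEs and SUSARs; the content is a set of utilisation and mortality counts. A trial report that follows 9.1 literally would present admissions, ICU nights and deaths as its serious-event result, and that result would differ in both directions from the SAEs that the protocol defines and the sites report.

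There is a second difficulty. The named safety endpoints are largely the same events that the vaccine is hoped to prevent. An all-cause count adds vaccine-caused events and subtracts prevented ones, so a neutral or favourable difference cannot by itself be read as absence of serious vaccine harm. Nothing else in 9.1, or in SAP Tables 1 to 5, separates the two.

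**Working it through.** The documents give no rate, count or power for any safety endpoint, so there is no figure of the plan's to reproduce. The main check sets the two definitions side by side.

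**1. Which events count where**

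| Event | SAE under protocol Safety section | Endpoint under SAP 9.1 |
|---|---|---|
| Death in follow-up | yes | yes |
| Non-elective stay of one night or more | yes | yes |
| Life-threatening event, survived, no night in hospital | yes | no |
| Lasting disability, no night in hospital | yes | no |
| Important medical event due to the intervention, no night in hospital | yes, on judgement | no |
| Elective stay of one night or more | no | yes |
| SUSAR | assessed case by case | no endpoint |

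Anaphylaxis shows the third row. The protocol's risk assessment names it among the severe but very rare effects. If it is treated and the participant goes home the same day, it can be an SAE under the protocol but meets none of the three SAP endpoints. A planned overnight procedure is the opposite case: it is a stay for medical reasons, and 9.1 does not repeat the elective exclusion.

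**2. Overlap with efficacy**

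The night-in-hospital wording in 9.1 is also the protocol's definition of its admission outcome (protocol, Outcomes). The overlap is close but not complete. The secondary outcome covers illness and leaves out accidents, while the safety endpoint takes any reason. The ICU and death endpoints coincide with all-cause items in the SAP's list of other outcomes.

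**3. How large the offset could be (illustration only)**

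Inputs: n = 1050 / 2 = 525 per arm (1:1 allocation, ignoring the planned 5% loss). The control admission risk p over six months is an assumption, taken from 1% to 10%. The reduction r = 0.20 is the plan's absenteeism hypothesis, and carrying it over to admissions is also an assumption.

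Vaccine-caused admissions that would leave the two arms equal = n × p × r:

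| p | Placebo admissions (525 × p) | Offset (525 × p × 0.20) |
|---|---|---|
| 1% | 5.25 | 1.05 |
| 2% | 10.5 | 2.1 |
| 3% | 15.75 | 3.15 |
| 5% | 26.25 | 5.25 |
| 10% | 52.5 | 10.5 |

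**4. What a relatedness row adds, and its limits**

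Take p near 3%, with 16 placebo admissions (15.75 rounded). With a 20% reduction the BCG arm has 12.6, rounded to 13. Add 6 vaccine-caused admissions: 13 + 6 = 19. Fisher's exact test, two-sided, 525 per arm:

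- all-cause, 19 v 16: p = 0.73
- related only, 6 v 0: p = 0.031
- related only, 5 v 0: p = 0.062
- related only, 3 v 0: p = 0.25

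The related count shows a pattern that the all-cause count hides. With fewer than about six events, even that comparison is imprecise, so such rows are mainly descriptive.

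**The case against.** The other side has good points.

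- **Same-day reactions are not lost.** A reader might infer that they would be missed altogether. The documents do not support that: 9.1 compares adverse events by arm, and the protocol sends every SAE to the sponsor and the DSMB within 24 hours. The gap is that such an event is not counted or tabulated as serious. The 24-hour notice is case by case. The scheduled monthly reports cover absenteeism by group (SAP, Statistical analysis) and admissions and deaths (protocol, Interim analysis), not SAEs by arm.
- **The offset does not come from leaving the protocol's definition.** A reader might infer that it does. The protocol's SAEs also include deaths and non-elective hospitalisations whatever their cause, so adopting that definition alone would leave the same offset. Only a split by relatedness addresses it.
- **Elective stays should fall about equally in both arms.** Under randomisation with blinded participants they add noise rather than bias. This stands; the issue is consistency with the protocol.
- **Section 9 of the SAP is labelled exploratory, and the data are collected.** This stands and limits the severity. It does not explain a heading that its content does not deliver.

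Two further inferences go beyond the documents. The protocol says of the severe reactions: "They are so rare that it would be unlikely with cases in the present trial of 1050 participants". A reader might set this against the frequency bands in the protocol's Intervention section and call it wrong. Those bands are followed by one pooled list that does not say which reaction belongs where. A single reaction at 1/1,000 gives 1 − (1 − 0.001)^525 = 41%, still below one half, and no analysis depends on the sentence. A reader might also infer that the birth-defect criterion can never be observed in 182 days. Self-reported pregnancy is an exclusion and no expected number of pregnancies is given. On an assumed 40-week term, one already at 14 weeks or more at enrolment would reach term (182 / 7 = 26; 40 − 26 = 14).

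**Conclusion.** The concern holds as a mismatch of definition and tabulation. SAP 9.1 does not deliver the SAE and SUSAR analysis that its heading announces. It leaves out serious events without an overnight stay, admits elective stays that the protocol excludes, and has no count by relatedness, although its endpoints largely overlap with outcomes that BCG is hypothesised to reduce.

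The mismatch rests on the text alone and needs no assumption. The size of the offset does need assumptions: about 1 to 10 admissions for an assumed control risk of 1% to 10%, and about 2 to 5 for 2% to 5%, each with an assumed 20% reduction. The documents supply neither an admission rate nor an effect on admissions, so these figures show only how the offset works. The point does not show that safety monitoring fails or that serious reactions go unrecorded. It should be corrected before the safety results are reported.

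**What to change.** In SAP 9.1:

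1. Define the SAE endpoint as participants with at least one SAE under the protocol's Safety section, elective admissions excluded, tabulated by arm.
2. Add separate rows by arm for SAEs judged related to the intervention, for SUSARs, and for each BCG reaction named in the protocol's Intervention and risk-assessment sections.
3. Keep all-cause admissions, ICU stays and deaths as outcomes in their own right, not as the SAE result.
4. State that counts are expected to be small and that the comparisons are mainly descriptive.

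Relatedness is a judgement, and BCG's local lesion can reveal the arm, so the related rows should be read beside the full SAE count and not replace it.

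The cost is SAP wording and one table. The protocol already requires SAEs and adverse events to be asked about every two weeks and SAEs to be assessed as possible SUSARs, so no new data collection is needed.
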